1.0 PURPOSE and OBJECTIVES

The purpose of this study is to compare the safety and efficacy of clobetasol propionate .05% ointment to fractional CO2 laser procedure for the treatment of vulvar lichen sclerosis.

Primary Outcome Measures:

- The primary outcome will be the subjective and objective cure of vulvar symptoms of itching, burning, dyspareunia at 12 weeks post treatment, or 6 months [Time Frame:12 weeks] using the SkinINDEX-29 and Vulvar Symptom Visual Analog Scale (VAS)

Secondary Outcome Measures:

- Complications [Time Frame: 6 week, 6 months, 1 year] pain, infection, de novo or worsening dyspareunia, contact dermatitis and burns
- Subjective Vulvovaginal Symptoms Questionnaire (VSQ)
- Objective Cure of Lichen Sclerosus [Time Frame:6 months, 1 year] using PHOTO documentation, Vulvar Signs Visual Analog Scale
- Health Related Quality of Life (HRQOL) based on patient global impression of improvement and satisfaction as well as the Vaginal Health Index [Time Frame: 6 months, 1 year]

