2.0 BACKGROUND and SIGNIFICANCE

Vulvar lichen sclerosis (LS) is a well-characterized dermatosis resulting in labial atrophy, synechiae and introital narrowing and can often cause dyspareunia, itching and co-existent vulvar pain. Biopsy is necessary to confirm the clinical diagnosis and the mainstay of treatment usually consists of topical steroid therapy.¹

Clobetasol propionate and mometasone furoate are potent topical steroids that have long been considered gold-standard treatment for vulvar lichen sclerosis and work through anti-inflammatory, anti-mitotic, and immunosuppressive effects. One of the complications of long-term steroid use, however, is potential thinning of the vulvar skin, therefore limiting long-term use. Other therapeutic options include topical calcineurin inhibitors, surgery including incision and skin graft treatment, cryotherapy and phototherapy. Table 1 summarizes current clinical comparative trials for lichen sclerosis involving topical steroid therapy. Clobetasol propionate has a range of efficacy from 61-91% depending on the selected outcome criteria.

Table 1.

Author/year	Study Design	N	Outcome	Results
Bracco, GL 1993 ²	RCT Clobetasol vs. testosterone vs. progesterone vs. cream based therapy	79	-Subjective scaled symptom remission of vulval LS -Objective histologic and gross improvement	-75% remission with Temovate versus 10% Progesterone, 20%Testosterone, and 10% cream based treatments had subjective remission of LS -Only Clobetasol propionate had significant histologic and gross improvement.
Terra S, 2014 ³	RCT clobetasol vs. phototherapy	15	-Mean relative reduction of total clinician's score (TCS): subjective pruritus and burning/pain VAS, Skindex-2, 20 MHz- ultrasonography, histopathological analysis	35.6% decrease in mean (total clinical score) TCS in UV-A1 phototherapy group -51.4% decrease in mean TCS for clobetasol propionate group; Skindex-29, pruritus, burning/pain significantly decreased -Phototherapy group's only significant difference was with burning/pain -Significant difference in dermal density on ultrasound and histopathological reduction of

				inflammatory infiltrate in clobetasol propionate group and not Phototherapy group

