Objective measures of the clinical appearance of vulvar lichen sclerosus will be completed by investigators at concurrent time points with the patient questionnaires. Non identifiable photo documentation of vulvar appearance will be completed using Fujifilm JX665 Digital Camera. Investigators blinded to treatment arm will complete visual assessment including white plaques/hypopigmentation, cigarette paper/thin skin, introital narrowing, perianal involvement (figure of eight shape), loss of labia minor, fusion of labia minora, phimosis of clitoral hood, vulvar fissure, and erosion scaled on validated visual analog scale, rated 0-10 from absent to severe, see appendix 1. Lower objective VAS scores corresponds to less severe Lichen Sclerosus disease. In addition, investigators will complete validated Vaginal Health Index (VHI) at all time points²¹, appendix 3. The VHI evaluates vulvovaginal overall elasticity, fluid secretion type and consistency, pH, epithelial mucosa, and moisture on a scale 1-5 from none to excellent. A lower VHI score corresponds to greater urogenital atrophy.

The laser used in this clinical investigation complies with federal laser performance standards.

Fractional CO2 laser with 10600 um wavelength, 60 W pulse, continuous or pulsed with repetition rate, articulated arm with scanner hand-piece, 120 Vac power and 635 nm aiming beam. The laser power will be set at 26 W, dwell time of 800 microseconds, DOT spacing at 800 micro meters and normal scan mode. Vulvar lichen sclerosis will be treated except for the clitoris glans and clitoral hood which will be spared with at least 5mm margin. The procedure will be performed in the outpatient clinic at the National Center for Advanced Pelvic Surgery at MedStar Washington Hospital Center or Medstar Lafayette Center, and include 3 sessions, 4 weeks apart. A minimum of 2 weeks are required from the time of biopsy to treatment. Prior to treatment eutectic local anesthetic (EMLA) will be applied for at least 5 minutes up to 30 minutes and then wiped off prior to laser treatment. Photodocumentation will take place at baseline and at 6 months and one year following the last LASER or STEROID treatment. Interpretation of photodocumentation with clinical objective scale will be completed by blinded provider.

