8.0 PROTECTION AGAINST RISK

The proposed study involves changes in provision of program services to study participants. Description of random and blinded nature of the protocols will be explained by the physician in charge of the participant. To avoid or minimize potential risks, frequent monitoring for adverse events will be performed by study staff and the PI.

Risks of clobetasol proprionate include skin irritation, burning, rash and change in skin pigmentation.

Potential adverse reactions to laser use include ocular laser exposure which will be minimized with the use of protective eyewear with an optical density of 4x the treatment wavelength. Pain or mild to moderate discomfort, erythema, swelling, blistering, itching, numbness, change in pigmentation, scarring, and burns are other adverse events including as well as painful intercourse, change (postive or negative) in sexual response, including arousal around clitoris and orgasm. These risks will be minimized with laser use per manufacture instructions with trained personel and avoidance of laser treatment within 5mm of clitoral glans and hood. All known risks will be disclosed to the participants via the informed consent process. All study participants will be closely monitored post treatment for adverse events.

All known risks will be disclosed to the participants via the informed consent process. All study participants will be closely monitored post treatment for adverse events. All study investigators will receive extensive training on the study protocol. Attending staff/surgeons will also receive training on how to operate the laser and the appropriate settings for the vulvar treatment, supervised by the study mentor. Serious adverse events are defined as any untoward medical occurrence that (1) results in death, (2) is life-threatening, (3) requires inpatient hospitalization (4) results in persistent or significant disability or incapacity, (5) is a congenital anomaly/birth defect, or (6) is another medically important condition.

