Appendix 1:

Subjective Symptoms VISUAL ANALOG SCALE (VAS)

Not bothersome	Most Bothersome
0 1 2 3 4 5 6 7 8	9 10

SYMPTOMS

Vulvar itching
 Vulvar burning
 Vulvar irritation
 Pain with intercourse
 Tearing of vulvar skin
 Painful urination
 Painful defecation

Objective Signs VISUAL ANALOG SCALE (VAS)

Absent		Mild		Moderate		Severe				
0	1	2	3	4	5	6	7	8	9	10

SIGNS

- White plaques/hypopigmentation
- Cigarette paper, thin skin
- Introital narrowing
- Perianal involvement (figure of 8 shape)
- Loss of labia minora
- Fusion of labia minora
- Phimosis of clitoral hood
- Vulvar fissure
- Erosion

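### The complications outcome is incomplete for both arms: it omits skin thinning, pigment change and scarring, all of which the protocol names as harms

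*Combined protocol and SAP*

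**What the plan says.** The stated purpose in Section 1.0 is to "compare the safety and efficacy of clobetasol propionate .05% ointment to fractional CO2 laser procedure". The secondary complications outcome, timed at 6 weeks, 6 months and 1 year, names five items: "pain, infection, de novo or worsening dyspareunia, contact dermatitis and burns".

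Section 2.0 says of the comparator: "One of the complications of long-term steroid use, however, is potential thinning of the vulvar skin, therefore limiting long-term use". Section 8.0 gives a different list for the same drug: "Risks of clobetasol proprionate include skin irritation, burning, rash and change in skin pigmentation". For laser, Section 8.0 lists pain, burns and painful intercourse, and also blistering, numbness, pigment change, scarring and altered sexual response, among others.

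Thin skin appears in Section 3.0 and Appendix 1 as one of nine objective signs rated 0 to 10 by a blinded assessor. The item on the form is "Cigarette paper, thin skin". Section 3.0 fixes how the scale is read: "Lower objective VAS scores corresponds to less severe Lichen Sclerosus disease". The scale feeds the objective-cure outcome, not the complications outcome.

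**The concern.** A safety comparison shows only the harms it is set up to tabulate. Here a harm that the protocol itself says limits the comparator is not on the list. It is recorded on a scale whose stated meaning is disease severity. A woman whose skin thins under treatment would be read as having worse lichen sclerosus, and in a total score her change could be cancelled by improvement in other signs.

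The steroid arm continues as needed after the three scheduled months, and follow-up runs to one year, so thinning is relevant to this trial. The laser arm has the same kind of gap: scarring and pigment change are disclosed as risks but are not in the outcome. A reader of the final report could see a complications table with no line for any of the three and take that as evidence that they did not occur.

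**Working it through.** **1. The plan's own figures.** The plan gives no rate, margin or power for complications. Its only design calculation is for Skindex-29: difference 16, SD 22, one-sided alpha 0.05, power 80% (Section 5.0). The normal approximation gives n = 2 × (1.645 + 0.842)² × 22² / 16² = 23.4, so 24 per arm, as stated. Recruitment is 52 at 1:1, which is 26 per arm.

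**2. Harms named in the protocol against the complications outcome.**

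| Harm | Named in | Arm | In the Section 1.0 list? |
|---|---|---|---|
| Skin thinning | 2.0 | steroid | no |
| Pigment change | 8.0 | both | no |
| Scarring | 8.0 | laser | no |
| Blistering, numbness | 8.0 | laser | no |
| Altered sexual response | 8.0 | laser | no |
| Rash, skin irritation | 8.0 | steroid | partly, as contact dermatitis |
| Pain, painful intercourse, burns | 8.0 | laser | yes |

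On the steroid side two named harms are missing outright (thinning, pigment change). On the laser side at least five are missing (blistering, numbness, pigment change, scarring, altered sexual response).

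**3. Whether another provision fills the gap.** Section 8.0 promises adverse-event monitoring for everyone but gives no term list, form or grading. The board described at the end of Section 8.0 reviews serious events, which gradual thinning would not ordinarily be. Section 12.0 gives tests by type of variable, with no item-level analysis of the signs.

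**4. How visible thinning is inside the signs scale.** No scoring rule is given, so assume a plain mean of nine items. A worsening of d points on thin skin moves the mean by d/9:
- d = 3: 3/9 = 0.33
- d = 5: 5/9 = 0.56

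A fall of 3 points on any one other sign would cancel the first of these exactly.

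**5. What naming the harm could show.** The documents give no thinning rate, so p below is assumed. The chance of at least one case among 26 women is 1 − (1 − p)^26. For a two-sided Fisher test at 0.05 against no cases in the other arm:
- 5 versus 0 gives P = 2 × C(26,5)/C(52,5) = 2 × 65,780/2,598,960 = 0.051
- 6 versus 0 gives P = 2 × C(26,6)/C(52,6) = 2 × 230,230/20,358,520 = 0.023

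Six cases are therefore needed, and power is the binomial chance of 6 or more in 26.

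| Assumed rate, steroid arm | Chance of at least one case | Fisher power against 0% |
|---|---|---|
| 5% | 74% | 0.2% |
| 10% | 94% | 4% |
| 20% | 99.7% | 42% |
| 30% | over 99.9% | 84% |

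Cases would probably be seen at quite modest rates, but only a large difference would be detected.

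**The case against.** The strongest reply is that thinning is already measured. A blinded assessor rates it at baseline, 6 months and 1 year, a higher score is worse, and worsening would count against whichever arm it occurred in. General monitoring could also pick it up. This stands against any claim that the plan cannot record thinning. It does not answer the narrower point, which is that the complications outcome would not tabulate it.

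A second reply is that the item is a disease sign, so its worsening may be treatment failure and not harm. Section 2.0 itself cites a randomised comparison with tacrolimus in which clobetasol reduced atrophic patches more. This also stands, and it is why the item should be reported without attribution.

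A reader might infer that the list is tilted against laser. The documents do not support that. Of the five items only burns are clearly specific to laser. Pain, infection and dyspareunia can be recorded in either arm, and contact dermatitis fits the topical product. The list also omits several laser harms. A reader might also infer that thinning is the reason for the trial. Section 2.0 calls it one potential complication of long-term use and never states it as the rationale, and the clobetasol risk list in Section 8.0 does not mention it.

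**Conclusion.** The point holds as a gap in both arms. Skin thinning, pigment change and scarring are harms by the protocol's own account and are absent from its complications outcome. Thin skin is captured only as one-ninth of a severity scale. The direction of any resulting imbalance between arms cannot be determined.

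This is a minor, inexpensive improvement to a secondary outcome. The dilution figures rest on an assumed mean of nine items, and the detection figures on assumed rates and 26 women per arm with complete follow-up. Neither is needed for the textual finding.

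**What to change.** Name skin thinning, pigment change and scarring in the Section 1.0 complications outcome, recorded in both arms, and reconcile the list with the harms in Sections 2.0 and 8.0.

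Report the existing blinded thin-skin item separately from the signs total: change from baseline and number worsened, by arm, at 6 months and 1 year. State in advance how many points count as worsened. Present it descriptively, without attributing change to disease or treatment.

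Record pigment change and scarring as adverse-event entries on the case report form. The existing pigment sign is rated jointly with white plaques, so it cannot serve as a proxy, and scarring has no rating at all. The signs scale has no 6-week rating, so thinning at that time point would also depend on a form entry.

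The cost is outcome wording, a few form fields and one table. The limits remain: disease and treatment effects on skin thickness cannot be separated, and the numbers support description only.

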3.0 STUDY DESIGN

Women presenting to the urogynecology clinic will be screened for lichen sclerosus. Vulvar biopsy will be performed for confirmation, and, if eligible, the patient will be consented to undergo baseline questionnaires, photodocumentation of vulvar lesions and randomization. Patient will be randomized to monthly LASER treatment for 3 months or topical STEROID therapy (temovate propionate .05% ointment nightly for one month, three times weekly for 2 additional months, then as needed) in a 1:1 ratio using a computer generated randomization schedule. Grouping assignments will be kept in sealed consecutively numbered, opaque envelopes. Because of the nature of the treatment, it will not be possible to blind patients but the assessor will be blinded to the intervention.

Patient questionnaires include multiple validated scales and surveys to provided reproducible measures of vulvar symptoms as primary and secondary outcomes. Questionnaires will be completed at the intake visit, repeated at 12 weeks after treatment is completed or 6 months from intake, and one year follow up. Subjective symptoms including vulvar itching, vulvar burning, vulvar irritation, pain with intercourse, tearing of the vulvar skin, painful urination, and painful defecation will be rated with a validated visual analog scale (VAS), scaled 0-10, see appendix 1. Higher values correspond to more bothersome symptoms. The Skindex-29 questionnaire is a subjective measure of skin symptoms validated against the Medical Outcomes Study 36-item Short-Form Survey (SF-36)¹⁷, appendix 2. The Skindex-29 was developed in dermatology and modified for use in vulvadynia¹⁸. The Skindex-29 is scored as a sum expressed on a 100-point scale with higher scores indicating lower quality of life. Validated quartiles are used to characterize disease symptoms, emotions, functioning, and overall score as either very little, mild, moderate, or severe¹⁹. Secondary outcomes of patient satisfaction and global impression of improvement will be collected using simple validated visual analog scale from 0-5, much worse to much better, appendix 4. A final subjective measure, the Vulvovaginal Symptoms Questionnaire (VSQ), a validated measure of vulvar symptoms, emotions, life impact, and sexual impact in postmenopausal women will be collected a secondary outcome²⁰, appendix 5. A higher total score on the VSQ corresponds to lower quality of life.

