5.0 SAMPLE SIZE CALCULATION

The study will consist of 2 study groups (LASER vs STEROID therapy). We expect improved subjective and objective results in the LASER group at 3 months post treatment or 6 months from enrollment compared with the STEROID group.

This study is designed as a two-group randomized clinical trial. Sample size calculations were conducted using the absolute change in the Skindex 29 as the primary end point. Our study will reach 80% power to detect a mean difference of 16 points on the Skindex 29 (sd=22 for both groups)²² between the study groups with 24 patients in each group, or 48 in total based on a one-sided two-sample t-test with alpha=0.05. By accounting for 10% attrition, we propose to recruit 52 patients to the study to be randomized with a 1:1 ratio to each group, with a blocked component for those who used topical clobetasol in the past. The Skindex-29 has validated cutoff categories for mildly, moderately, and severely impaired health related quality of life scores, the mean difference between each quality of life measure overall score is between 6 and 7. Therefore, powering the study for a detection of mean difference of 16 points should measure significant quality of life improvement.^{23,24}

Study Timeline:

	Intake Visit	Day 0	2 weeks	4 weeks-14 weeks	6 months	1 year
Vulvar biopsy (if never completed)	X					
Vaginal STEROID or LASER			STEROID daily x 4 weeks LASER monthly x 3 months	STEROID three times weekly x 8 more weeks, then as needed LASER STOP at 12 weeks		
Vaginal Health Index scale (VHIS)		X			X	x
SkIndex-29 Vulvar QoL Questionnaire Vulvovaginal Symptoms Questionnaire (VSQ)		X			X	x
Telephone call to check compliance and answer questions			X	X (8 weeks)		
Photodocumentation		X			X	x
Questionnaire of patient global impression of improvement and satisfaction PGI-I					X	x

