12.0 STATISTICAL ANALYSIS

Statistical intention-to-treat and per protocol analysis will be completed in R (version 3.4, Vienna, Austria 2017) with demographic and questionnaire scores reported as means and standard deviations or medians and interquartile ranges. Chi square or Fisher's exact, two-sample t-test and Mann Whitney U will be used to compare categorical, continuous, and non-parametric variables, respectively. D-Agostino test will be used to assess normality. Two-way ANOVA analysis of mean Skindex-29 score improvement based on prior steroid exposure and treatment group will be performed.

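### The sign outcome is labelled a cure although its instrument is a graded 0-10 rating of nine signs; no cure rule or test is assigned, and every listed group comparison leaves out the baseline rating

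*Combined protocol and SAP*

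**What the plan says.** Section 1.0 lists among the secondary outcomes "Objective Cure of Lichen Sclerosus [Time Frame:6 months, 1 year] using PHOTO documentation, Vulvar Signs Visual Analog Scale". Section 3.0 describes the instrument: nine named signs, "scaled on validated visual analog scale, rated 0-10 from absent to severe", with the direction given as "Lower objective VAS scores corresponds to less severe Lichen Sclerosus disease". Appendix 1 sets out the same nine signs on the same 0-10 line. Section 3.0 places the objective ratings at the same time points as the questionnaires, namely intake, 6 months and one year, and states that "Investigators blinded to treatment arm will complete visual assessment".

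Section 12.0 assigns tests by type of variable only: "Chi square or Fisher's exact, two-sample t-test and Mann Whitney U will be used to compare categorical, continuous, and non-parametric variables, respectively". It names one specific model, a two-way ANOVA of mean Skindex-29 improvement by treatment and prior steroid exposure. The signs are not mentioned there. No section gives a cure threshold, a total score or an analysis for the signs.

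**The concern.** A cure is ordinarily a yes/no result, whereas the instrument behind this one is graded. The plan does not say which of the two will be compared, and each route has a cost.

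- **Analysed as cured/not cured.** Much of the information in a nine-item 0-10 rating is discarded in a trial with about 24 evaluable women per arm. With no threshold fixed in advance, the cut could also be chosen after the data are seen.
- **Analysed as a score.** The t-test and Mann-Whitney test listed in Section 12.0 do not adjust for the baseline sign rating, which Section 3.0 already collects.

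This outcome carries particular weight. Section 3.0 says of blinding that "it will not be possible to blind patients but the assessor will be blinded to the intervention", and the symptom scales are all self-reported. The sign rating is the only efficacy measure whose own description says that blinded raters complete it. A null cure result from an underpowered comparison could be misread as evidence that the laser has no objective effect.

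**Working it through.** **1. Inputs.** From Section 5.0: difference 16 points, SD 22, 24 per group, one-sided alpha 0.05, 80% power, all for the Skindex-29. The documents give no effect size, SD or cure rate for the signs. I therefore assume that the signs have the same standardised effect, d = 16/22 = 0.727, and are roughly normal. The steroid-arm cure rate is varied.

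**2. The plan's own figure.** Noncentral t with 2 × 24 − 2 = 46 degrees of freedom and noncentrality 0.727 × √(24/2) = 2.52 gives power of 79.9% one-sided. This reproduces the stated 80%. The two-sided figure is 69.4%.

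**3. The same effect, cut to yes/no.** If a proportion p0 is cured on steroid, the same shift gives p1 = Φ(Φ⁻¹(p0) + 0.727) on laser. Power comes from exact enumeration of two binomials with n = 24 each, one-sided 5%; chi-square is uncorrected.

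| Steroid p0 | Laser p1 | Chi-square power | Loss (points) | Fisher power | Loss (points) |
|---|---|---|---|---|---|
| 10% | 29% | 52.5% | 27.4 | 39.4% | 40.4 |
| 20% | 45% | 59.8% | 20.1 | 48.1% | 31.8 |
| 36% (best cut) | 64% | 65.8% | 14.1 | 54.3% | 25.6 |
| 50% | 77% | 61.9% | 18.0 | 50.1% | 29.7 |
| 61% | 84% | 57.1% | 22.8 | 45.5% | 34.4 |
| 67% | 88% | 54.6% | 25.2 | 42.5% | 37.4 |
| 77% | 93% | 48.3% | 31.6 | 32.5% | 47.3 |
| 91% | 98% | 24.8% | 55.0 | 4.2% | 75.7 |

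The best cut is the symmetric one, p0 = Φ(−0.727/2) = 0.358. So 14 and 26 points are floors under this effect, and there is no natural ceiling. The 61% and 91% rows span the clobetasol efficacy range in Section 2.0. The 67% row matches an objective response (75% improvement criterion) in one trial in Table 1. None of these is a cure rate on this trial's scale.

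Section 12.0 does not say whether secondary tests are one-sided. With two-sided tests the smallest losses are 15.1 points (chi-square) and 27.0 points (Fisher).

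**4. Sensitivity to the borrowed effect.** With d varied from 0.4 to 1.0 and the most favourable cut chosen each time, the smallest loss is about 8 points (chi-square) or 16 points (Fisher). At d = 0.5 it is 11 and 22 points.

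**5. If a score is analysed instead.** Let ρ be the correlation between baseline and follow-up sign scores, with equal variances. Adjusting for baseline multiplies the variance of the treatment difference by 1 − ρ² relative to an unadjusted follow-up comparison. Relative to an unadjusted change-score comparison, the factor is (1 − ρ²)/(2(1 − ρ)) = (1 + ρ)/2. The documents do not give ρ. For assumed values of 0.3, 0.5 and 0.7 the factors are 0.91, 0.75 and 0.51 against follow-up, and 0.65, 0.75 and 0.85 against change. The adjusted model is the more precise in each case, apart from the one degree of freedom it uses.

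**The case against.** The strongest reply is that no yes/no outcome has been declared. A reader might infer one from the word cure, but the documents do not support that as fact. Section 1.0 also calls the primary outcome a cure, and yet Section 5.0 states that "Sample size calculations were conducted using the absolute change in the Skindex 29 as the primary end point" and Section 12.0 plans an ANOVA of mean improvement. Where the analysis of a so-called cure can be checked in this plan, it is graded. Section 12.0 assigns no test to the signs, and a 0-10 rating fits its t-test or Mann-Whitney category. This stands: the power loss is conditional on dichotomising and is not a loss to which the plan commits itself.

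Two further readings are tempting and should be resisted.

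- **A fixed range of loss, such as 14 to 47 points.** The lower figure is a floor under a borrowed effect. The upper is simply Fisher's test at a 77% steroid rate, and the loss grows beyond it. The effect comes from a patient-reported quality-of-life scale, and no power is claimed for this secondary outcome.
- **That this is the trial's only blinded efficacy comparison.** Section 3.0 says that "In addition, investigators will complete validated Vaginal Health Index (VHI) at all time points". The index is a listed secondary outcome, and the general statement on assessor blinding may cover it. Only the sign and photograph rating is expressly called blinded, which does not show that the index is rated unblinded.

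The objection does not remove the need to act. If a graded analysis was intended, the text does not say so, and the tests it lists for group comparison would still leave out the baseline rating.

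**Conclusion.** The point holds in conditional form. The outcome's label and its instrument do not match, and neither a cure rule nor an analysis is specified. A literal cured/not-cured analysis would cost at least about 14 points of power by chi-square or 26 by Fisher's exact test, and more away from central cure rates. Those figures rest on d = 16/22, approximate normality, 24 per arm and a one-sided 5% test. A score analysis with the listed tests avoids that loss but gives up precision that baseline adjustment would recover; how much depends on a correlation the documents do not give. On either reading a graded, baseline-adjusted comparison is the better analysis of data already being collected. As this is a secondary outcome with no stated power, the change should be made but does not bear on the sample size.

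**What to change.** - **Section 1.0:** replace the cure wording with the Vulvar Signs VAS score at 6 months and 1 year, read by blinded raters. Define it as a pre-specified total of the rated signs. If all nine are summed, the range is 0 to 9 × 10 = 90. The sponsor should state which signs enter the total.
- **Section 12.0:** compare the arms on this score by a linear model with treatment and baseline Signs VAS score as covariate, reporting the mean difference and 95% CI. Give any proportion cured descriptively only, with its threshold fixed in advance.
- **Description of blinding:** refer to the sign rating as the only efficacy measure explicitly said to be blinded-rated, and state whether the Vaginal Health Index is also rated blind.

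The cost is wording. No extra visits, patients or data are needed, because Section 3.0 already has the signs rated at intake, 6 months and one year. The small downside is that a mean score difference is less immediate to read than a cure rate, which is the reason to keep the proportion as a description.
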